C5. Randomization. **a. Primary Tailoring Variable (PTV):** The PTV determines the set of randomized intervention options. Thus, the PTV in any SMART must be a proximal measure of the outcome that denotes early success or failure and can be implemented in practice²⁸. In this SMART, the PTV is a predetermined benchmark for adequate implementation. This benchmark will be based on C-SSRS Screener fallouts and CSRE fallouts. The cut-off for both must be 80% or higher (i.e., less than 20% fallouts) to be considered adequate implementation. This cut-off was chosen with input from the program partner and previous QI projects with the program office that involved setting implementation benchmarks (i.e., REACH VET implementation). This benchmark is meant to represent a performance target that all facilities are expected to work towards. Preliminary data indicates that, across facilities since October 2018, the 1st quartile of C-SSRS fallouts is 47.9% (range: 12.9% - 87.4%), and the 1st quartile of the CSRE fallouts is 61.2% (range: 12.5% - 100%). 75% of sites currently have C-SSRS and CSRE fallout percentages greater than 47.9% and 61.2%, respectively. Based on these numbers at least 80-90% of sites currently do not meet criteria for adequate performance. We expect that this number to decrease some as implementation continues, but we expect that many sites will still have significant room for improvement when this project begins. The program partner may adjust this benchmark based on additional data gathered. **b.** Randomization procedures: Randomization will occur at the site level. VAMCs that are not meeting the benchmark for adequate implementation (See PVT above) at Baseline month 6 will be randomized 1:1 (R1) to receive A/F or continued IAU for 10 months. A/F sites that do not meet the benchmark for adequate implementation at the 10th interventional month will be randomized 1:1 (**R2**) to either continue A/F or augmentation with EF (A/F + EF) for an additional 10 months. A/F sites that meet the criteria for adequate implementation will be randomized 1:1 (**R3**) to either continue A/F or discontinue A/F and return to IAU. R1 will be stratified by facility complexity level (i.e., high, medium and low) and level of performance (i.e., low or moderate) at baseline. The Facility Complexity Model²⁹ classifies VA medical facilities at levels 1a, 1b, 1c, 2, or 3. Level-1a facilities are the most complex and level-3 facilities are the least complex. Levels 1a-1c will be considered high complexity, level 2- medium complexity and level 3- low complexity. Approximately 61% of facilities (N=85) are high complexity, 17% (N=24) are moderate and 22% (N=31) are low complexity. Additionally, the average of the C-SSRS Screener and CSRE fallout rates for the 6th Baseline month will be calculated for each facility to be randomized (R1) and the median of these averages will be used to determine stratification by level of performance (i.e., low – above median fallout rate, or moderate – below median fallout rate). R2 will also be stratified by facility complexity level and level of performance (based on the median of the fallout rate at the 10th month of phase 1). R3 will be stratified only by facility complexity level as all sites will have met the benchmark. These procedures will ensure that intervention groups are balanced for site variables that may correlate highly with outcomes. If less than 12 sites will be randomized at R2, stratification will only occur based on facility complexity, unless all facilities are at the same level of complexity in which case only median level of performance will be used for stratification.

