EPRP outcomes of change in sui2 and csra1 from the 6th month of the baseline period to the 10th month of the first interventional phase will each be modeled as a function of group (A/F vs. IAU), the baseline outcome value, the stratification variables of facility complexity (high, medium, low) and baseline performance level (above or below the median average fallout rate), and geographic region (West, Midwest, Southwest, Southeast and Northeast). Inference will be made based on the coefficient associated with the group variable and 97.5% confidence intervals (CI) will be reported (alpha=0.025). A similar analysis will be used to determine the effect of A/F on the change in the EPRP outcome for the primary screeners (sui40 and sui51), with 95% CIs reported. **c.** Secondary Aims: 1). To test the effect of the addition of EF for those who do not implement adequately at end of interventional phase 1, the primary EPRP outcomes of change in sui2 and csra1 from the 10th month of interventional phase 1 (baseline for interventional phase 2) to the 10th month of interventional phase 2 will be modeled as a function of group, the baseline outcome value, the stratification variables and geographic region (if sample sizes allow for control of this variable). Inference will be made based on the coefficient associated with the group variable and 95% CIs will be reported. A similar analysis will be used to determine the effect of the addition of EF on the change in the EPRP outcome for the primary screeners (sui40, sui51), with 95% CIs reported. 2). An analysis similar to that described for secondary aim 1 will be employed to investigate the effect of discontinuing A/F for those who implemented adequately at the end of interventional phase 1. Lastly, we will use a data driven approach to characterize each of the four EPRP outcomes over time for each group outlined in Figure 2 (group 1-6). Mixed effects models with a random intercept and slope will be used to model each of the four EPRP outcomes as a function of categorical group (1-6) and an interaction between group and a Bspline transformation on time (allowing the outcome to vary smoothly over time, using 21-time points, i.e., the 6th baseline month and every month of each interventional phase) such that each group will have its own trajectory. The trajectory for each group will be plotted with pointwise confidence intervals. **d. Exploratory** Aims: *i. Reach*: Reach will be calculated using the following formula: actual number of Veterans screened or evaluated/ actual number of Veterans eligible for screening, calculated cumulatively across all three study phases and all sites. We will calculate reach for each assessment stage of VA Risk ID. We will examine representativeness of patients reached by comparing demographic characteristics and other relevant variables (e.g., settings in which screening was completed) between eligible Veterans who were screened and/or evaluated and those who were not. Given that Veterans are clustered within facility, if the intra-class correlation between Veterans within each facility is estimated to be greater than zero, methods appropriate for clustered data will be employed to compare the variables of interest. For continuous variables, linear mixed models will be used with a random facility effect and non-normal data will be transformed. For binary variables, generalized linear mixed models will be used with a logit link and for categorical variables, random effects multinomial models will be employed. If the ICC is zero, t-tests, Wilcoxon rank-sum, Chi-square or Fisher's exact tests will be used, as appropriate. *ii. Adoption & Implementation Factors:* Key informant interviews will be used to examine factors influencing adoption of the implementation interventions and barriers and facilitators of implementing VA Risk ID to fidelity. All qualitative data sources, including interview transcripts and documents will be compiled and managed using Nvivo V. 9.0 software. We will take a general inductive approach³⁴. Specifically, data analysis will be determined by both the research objectives (i.e., domains of the RE-AIM framework) and multiple readings and interpretation of the raw data (i.e., content analysis). The goal is to establish clear links between the research objectives and the summary findings derived from the raw data. *iii. Effectiveness- Clinical Innovation:* We wish to examine whether Veterans who receive the CSRE are more likely to receive a safety plan within 2 weeks than those who screen positive on the primary screen only. To account for clustering of Veterans within facility, a mixed-effects logistic regression will be used to model the outcome of safety plan within 2 weeks (yes/no) as a function of group (receipt of CSRE/positive on primary screen only) with a random subject within facility effect. Additionally, to determine if receipt of a timely safety plan depends on whether Veterans are considered to be at low, moderate or high acute risk of suicide, this model will be repeated with the addition of a group by (categorical) acute risk interaction. Odds ratios for receipt of CSRE relative to positive on primary screen only will be reported for each level of acute risk with 95% confidence intervals.

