Examining the Effectiveness of an Adaptive Implementation Intervention to Improve Uptake of the VA Suicide Risk Identification Strategy (PEC 19-303)

NCT04243330

October 17, 2024

QUERI RISK ID Statistical Analysis

Primary Aim. Determine if the addition of Audit and Feedback in Phase 1 (February 2021 – November 2021) significantly improved eCSSRS1 and eCSRE1 adherence. To determine the effect of Audit & Feedback on Phase 1, we compared group 6 (Implementation As Usual [IAU] in Phase 1; N=66) to Groups 2, 3, 4, and 5 combined (Audit & Feedback [AF] in Phase 1; N=67). We used all available data and modeled monthly 1) eCSSRS1 and 2) eCSRE1 adherence across the entire study period (January 2021 – March 2024) for each group (IAU and AF). We chose to estimate these trajectories using natural cubic B-spline transformations on time to allow for smoothly changing trajectories and not restrict the estimation to a parametric form (e.g., polynomials). Internal knot selection for the B-splines was based on visible change points in descriptive longitudinal plots – these were November 2021, January 2022, November 2022, and March 2023 (or months 11, 13, 23, and 27). These 4 internal knots result in 5 knot spans and 5 degrees of freedom for each group/outcome combination modeled. Each outcome was then modeled as a function of group, the B-spline transformations, and group by B-spline transformation interactions so that we could estimate a trajectory for each group. These mixed effects models included a random intercept (i.e., random site effect). Contrasts were constructed within each model and were used to estimate the change in adherence for each group from February 2021 – November 2021 and the difference in adherence change between the groups, which was our hypothesis test of interest. These estimated differences in change were reported with 95% confidence intervals (CIs). For both estimates, the difference in change was calculated as the AF group minus the IAU group.

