Secondary Aim 2a. For sites that responded to AF during Phase 1, determine if switching to AF Light during Phase 2 (January 2022 – July 2023) resulted in a significant decrease in eCSSRS1 and eCSRE1 adherence. To determine the effect of switching to AF Light in Phase 2, we compared Group 2 (Continued AF; N=6) to Group 3 (Switched to AF Light; N=6). We used the same approach as was used for the Primary Aim. Monthly eCSSRS and eCSRE adherence was modeled across the entire study period as a function of group (Continued AF and Switch to AF Light), B-spline transformations on time, and group by B-spline transformation interactions, so that we could estimate a trajectory for each group. Knot selection was the same as for the Primary Aim. Contrasts were constructed within each model and were used to estimate the change in adherence for each group from January 2022 – July 2023 and the difference in adherence change between the groups, which was our hypothesis test of interest. These estimated differences in change were reported with 95% Cls. For both estimates, the difference in change was calculated as the Continued AF group minus the Switch to AF Light group.

Secondary Aim 2b. For sites that did not respond to AF during Phase 1, determine if the addition of External Facilitation (EF) during Phase 2 (January 2022 – July 2023) resulted in a significant increase in eCSSRS1 and eCSRE1 adherence. To determine the effect of the addition of EF in Phase 2, we compared Group 4 (Continued AF; N=38) to Group 5 (Added EF; N=17). We used the same approach as was used for the Primary Aim. Monthly eCSSRS and eCSRE adherence was modeled across the entire study period as a function of group (Continued AF and Added EF), B-spline transformations on time, and group by B-spline transformation interactions, so that we could estimate a trajectory for each group. Knot selection was the same as for the Primary Aim. Contrasts were constructed within each model and were used to estimate the change in adherence for each group from January 2022 – July 2023 and the difference in adherence change between the groups, which was our hypothesis test of interest. These estimated differences in change were reported with 95% CIs. For both estimates, the difference in change was calculated as the Continued AF group minus the Added EF group.

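### The SAP's tests of change rest on a model whose only stated site term is a random intercept, which cancels from the tested contrast, so 95% coverage is not assured

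*SAP*

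**What the plan says.** In the SAP, Primary Aim, adherence is modelled on group, a natural cubic spline on time and their interaction: "We used all available data and modeled monthly 1) eCSSRS1 and 2) eCSRE1 adherence across the entire study period", January 2021 to March 2024. The site term is given in one sentence: "These mixed effects models included a random intercept (i.e., random site effect". The tested quantity is "the difference in adherence change between the groups, which was our hypothesis test of interest", from February to November 2021, with 95% confidence intervals. The arms are 66 sites on usual implementation and 67 on audit and feedback, the latter being "Groups 2, 3, 4, and 5 combined (Audit & Feedback [AF] in Phase 1; N=67".

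Secondary Aims 2a (6 v 6 sites) and 2b (38 v 17) test the change from January 2022 to July 2023: "We used the same approach as was used for the Primary Aim". The SAP states no residual covariance, standard-error method or degrees of freedom.

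The protocol planned otherwise. Section C2 makes the site the unit of randomisation. Section C7 b regresses one value per site, "change in sui2 and csra1 from the 6th month of the baseline period to the 10th month of the first interventional phase", on group, baseline, stratification factors and region. For its descriptive spline trajectories (C7 c) it specifies a random slope as well as a random intercept. The SAP gives no reason for naming only the intercept.

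**The concern.** A random intercept lets sites differ in level. It does not let them differ in how they change, and change is what is tested. If the intercept is the only site term, a site that drifts away from its arm's curve is recorded as a run of independent monthly errors. The test then uses month-to-month noise as its yardstick, although sites were randomised.

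If residuals are positively correlated from month to month, a strategy with no effect would be declared effective (or, in 2a, its withdrawal harmful) more often than 5% of the time, in all three tests. Differing site slopes do the same in 2a and 2b, which have few sites and an 18-month window. Readers cannot tell how far this applies, because the SAP neither describes the variance estimation nor plans a site-level check.

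**Working it through.** **The protocol's own figures.** A two-sample t-test on one change value per site, SD 0.10, 80% power, gives detectable differences of 0.0589 (N=112) and 0.0555 (N=126) at alpha 0.025, and 0.0762 (N=56) and 0.0717 (N=63) at 0.05. C7 a states 0.059, 0.055, 0.076 and 0.072, so these reproduce. The protocol's precision was reckoned per site. The SAP gives no comparable figure.

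**Inputs.** From the SAP: 39 months; internal knots at months 11, 13, 23 and 27; windows month 2 to 11 (primary) and 13 to 31 (2a, 2b); the site counts above. Assumed: boundary knots at months 1 and 39, complete data unless stated, and all variances. The residual SD of 0.071 is 0.10/√2 and serves only as a scale. The protocol's 0.10 comes from one quarter of a similar measure, so 0.05–0.15 is shown.

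**Step 1: the intercept cancels.** Each arm's estimated change is w'ȳ, with ȳ the vector of monthly arm means. Building the spline gives w'1 = 0 in both windows, w'w = 0.4795 (primary) and w'w = 0.2321 (2a, 2b). A constant per site therefore adds nothing to the variance. With 20% of months missing at random it still supplies under 0.03%.

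**Step 2: model and true standard errors.** With S the within-site covariance:
- model SE² = E[s²] · w'w · (1/n₁ + 1/n₂)
- true SE² = w'Sw · (1/n₁ + 1/n₂)
- ratio R = √(w'Sw / (E[s²] w'w)); type I error = 2(1 − Φ(1.96/R))

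Site divergence also enters s², so it inflates the model SE to some extent, but spread over all 39 months.

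**Step 3: serial correlation.** The residual SD cancels here. At AR(1) 0.3, R is 1.27 / 1.37 / 1.36.

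| AR(1) | Primary | 2a | 2b |
|---|---|---|---|
| −0.1 | 3.4% | 3.0% | 3.0% |
| 0 | 5% | 5% | 5% |
| 0.05 | 6.0% | 6.3% | 6.2% |
| 0.1 | 7.0% | 7.7% | 7.6% |
| 0.3 | 12.3% | 15.3% | 15.1% |
| 0.5 | 18.9% | 26.1% | 25.4% |

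With 20% of months missing at random: 11 / 14 / 13% at 0.3 and 16 / 24 / 22% at 0.5.

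**Step 4: linear site slopes.** Take a slope SD of 0.10 over the 38 month-steps and residual variance 0.005 (SD 0.071). A linear slope passes through the contrast as 9/38 = 0.237 (primary) or 18/38 = 0.474 (2a, 2b).
- Primary: w'Sw = 0.01 × 0.237² + 0.005 × 0.4795 = 0.00296. E[s²] = 0.00589, so the model uses 0.00589 × 0.4795 = 0.00282. R = 1.02; type I error about 5.5%.
- 2a: w'Sw = 0.01 × 0.474² + 0.005 × 0.2321 = 0.00340. E[s²] = 0.00577, so the model uses 0.00134. R = 1.59; type I error 22%.
- 2b: 21% by the same route.

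Slope SDs of 0.03–0.20 give 5.1–6.5% (primary), 6.8–40% (2a) and 6.8–39% (2b).

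**Step 5: shape of divergence and residual SD.** Type I error with divergence SD 0.10, for residual SD 0.05 to 0.15:

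| Divergence | Primary | 2a | 2b |
|---|---|---|---|
| Linear throughout | 6.0–5.1% | 31–10% | 30–10% |
| Only after month 13 | 1.8–4.4% | 43–14% | 42–14% |
| Only up to month 11 | 39–12% | 2.7–4.7% | 2.5–4.6% |

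**Step 6: cross-checks.** On another scaling (SD of the raw two-month change fixed at 0.10, a quarter of its variance being true linear site divergence), coverage is 93.1% (primary), 73.0% (2a) and 73.6% (2b). Simulation of the stated model at AR(1) 0.3 gave 12.2 / 15.6 / 15.9%. In 38 simulated settings, half with 20% of months missing and 4,000 runs each, Welch's test on one spline contrast per site gave 4.1–5.6%.

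**The case against.** The SAP is a short account in the past tense. Saying that the models had a random intercept does not say that they had nothing else, and an unreported robust standard error would remove the problem. This stands as a limit: what is established is the stated model and its consequence, not what the software did.

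All sizes are assumed, and results run from 1.8% to 43% with the shape chosen. That is also true. The ranges show that validity depends on an unchecked assumption; they do not estimate this trial's error rate. The primary test is least exposed: near nominal under linear slopes and conservative under late divergence. It is inflated by positive serial correlation or by divergence within Phase 1, neither of which the documents show.

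Pooling Groups 2–5 in the primary audit-and-feedback arm means its sites receive different Phase 2 strategies and need not run parallel. With Phase 2 effects of 0.076, however, this moves the primary test only to 4.6%, so it illustrates the assumption and adds no inflation.

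Finally, the protocol's adjusted regression was specified in advance, so one may prefer it as the main test. That is reasonable, since it also uses the site as error unit. The site-level spline contrast is put first because, with complete data, it keeps the SAP's point estimate. Both should be reported.

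**Conclusion.** The concern holds. As stated, the model gives 95% coverage only if sites within an arm run parallel and months are independent given site, and nothing in the SAP supports or checks either condition. The cancellation is exact with complete data. The size is unknown because the documents give no serial correlation or slope variance. Positive serial correlation inflates all three tests. Linear slopes matter for 2a and 2b and hardly for the primary aim. Divergence limited to one phase can make a test too liberal or too conservative. This should be fixed; confidence is medium, because variance estimation may have been fuller than reported.

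**What to change.** 1. For all three comparisons, compute the SAP's spline contrast for each site and compare arms by t-test, with Welch as default. In 2b, slopes of SD 0.10 in the 17-site arm alone give 11.0% with the pooled t and 5.4% with Welch. State how sites with missing months enter.
2. As confirmation, report the protocol's baseline-adjusted regression of one change value per site. With all covariates it leaves 133 − 10 = 123 residual df (primary) and 55 − 10 = 45 (2b). In 2a, where "R3 will be stratified only by facility complexity level as all sites will have met the benchmark", baseline, complexity and region leave 12 − 9 = 3 df (critical t 3.18), while group plus baseline leaves 9 (2.26). The protocol already makes region conditional on sample size ("the stratification variables and geographic region (if sample sizes allow for control of this variable"), so fix the reduced 2a set explicitly.
3. If the mixed model stays as the main test, state its residual covariance, standard-error method and df. Use cluster-robust standard errors by site with a small-sample correction and Satterthwaite site-level df; these gave 4.1–5.6% in the same simulations. Weaker repairs fall short:
   - uncorrected robust errors with z give about 10–11% in 2a;
   - changing only the df to n − 2 leaves 12 / 10 / 15% at AR(1) 0.3;
   - a random slope with AR(1) residuals gives 26% for the primary test under divergence up to month 11, and 7 / 9% for 2a / 2b under divergence after month 13.

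The cost is SAP wording and a re-run on existing data. If the SAP's assumptions hold and data are complete, a t-test on 131, 10 and 53 df widens the interval by about 1%, 14% (half-width 0.039 to 0.044 at residual SD 0.071) and 2%; with Welch, 2b is about 4% wider (about 31 df). With 20% of months missing at random, the standard error is a further 5%, 1% and 2% larger.

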
C7. Analyses. a. Sample Size and Power Calculations: Power was calculated using the two-sample ttest procedure in Power and Sample Size (PASS 16). As there are two primary EPRP outcomes (sui2 and csra1), alpha is set to 0.025. The FY2018 first quarter numbers for a similar EPRP (sre1, timely SRE if positive PTSD or MDD screen) across 140 facilities was used to obtain an estimated standard deviation for sui2 and csra1 of 0.10. Power was calculated for two scenarios given the preliminary fallout data noted above. Assuming proportions of 0.8 and 0.9 not adequately implementing at month 6 of the run-in phase such that N=112 and N=126 are eligible for randomization at R1, this would provide 80% power to detect a difference in change between A/F and IAU of 0.059, and 0.055, respectively. Regarding secondary aim 1, assuming alpha=0.05, SD=0.10, and facilities eligible for randomization at R2 of 56 and 63, there is 80% power to detect a difference in change between continued A/F and A/F + Facilitation of 0.076 and 0.072, respectively. Given the same assumptions for secondary aim 2 as used for secondary aim 1, the detectable differences in change are the same for examining continued A/F versus discontinued A/F. **b. Primary Aim:** Using linear regression, the primary

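### The SAP reports both primary outcomes with 95% CIs, although the protocol set alpha 0.025 and 97.5% CIs because there are two of them

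*SAP*

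**What the plan says.** Protocol, C7.a (Sample Size and Power Calculations), sets the level and gives the reason: "As there are two primary EPRP outcomes (sui2 and csra1), alpha is set to 0.025". C7.b (Primary Aim) carries it into the analysis: "Inference will be made based on the coefficient associated with the group variable and 97.5% confidence intervals (CI) will be reported (alpha=0.025".

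The protocol distinguishes the primary outcomes from the rest. For the primary screeners C7.b specifies "the EPRP outcome for the primary screeners (sui40 and sui51), with 95% CIs reported", and C7.c uses 95% for the secondary aims.

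The SAP's Primary Aim still has two outcomes. It asks whether Audit and Feedback (A/F) "significantly improved eCSSRS1 and eCSRE1 adherence", and for each outcome it identifies "the difference in adherence change between the groups, which was our hypothesis test of interest". It then states "These estimated differences in change were reported with 95% confidence intervals (CIs". Secondary Aim 2b uses the same level: "These estimated differences in change were reported with 95% CIs". Nowhere does the SAP give an alpha, a correction, a testing order or a reason for leaving 97.5%.

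**The concern.** Dividing 0.05 between two outcomes makes sense only if either one alone can support a claim of benefit, and that is the situation in which multiplicity has to be controlled. The SAP keeps two primary tests but uses the interval level that the protocol reserved for outcomes without that protection. A reader given a question about significant improvement, a 95% interval and no other threshold will judge by whether the interval excludes zero.

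The primary conclusion depends on this whenever either p-value lies between 0.025 and 0.05: the SAP would then count an effect of A/F that the protocol would not. The SAP is dated October 2024 and its data run to March 2024, so the looser level is documented only after data collection ended.

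**Working it through.** **Inputs.** From protocol C7.a: alpha 0.025, 80% power, N = 112 or 126, and an "estimated standard deviation for sui2 and csra1 of 0.10". From C5: 1:1 randomisation. From the SAP Primary Aim: 66 sites on implementation as usual and 67 on A/F, two outcomes, 95% CIs. The documents give no correlation between the outcomes, so I assume values from 0 to 0.9.

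**1. Reproduce the protocol's power figures.** Two-sample t-test (noncentral t), SD 0.10, equal arms, 80% power. The protocol does not state sidedness; two-sided reproduces its figures.

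| N | Protocol | Two-sided 0.025 | Two-sided 0.05 |
|---|---|---|---|
| 112 | 0.059 | 0.0589 | 0.0534 |
| 126 | 0.055 | 0.0555 | 0.0503 |

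The stated detectable differences match 0.025 and not 0.05, so the 0.025 level was actually used in the power statement.

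**2. Chance of a false finding on at least one outcome.**

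For independent outcomes, in either direction:
- 0.05 each: 1 − (1 − 0.05)² = 0.0975
- 0.025 each: 1 − (1 − 0.025)² = 0.0494
- ratio: 0.0975 / 0.0494 = 1.97

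For independent outcomes, counting only false findings in favour of A/F:
- 0.05 each: 1 − (1 − 0.025)² = 0.0494
- 0.025 each: 1 − (1 − 0.0125)² = 0.0248

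For correlated outcomes, from the bivariate normal distribution:

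| Assumed correlation | Either direction, 0.05 each | Either direction, 0.025 each | Favouring A/F, 0.05 each | Favouring A/F, 0.025 each |
|---|---|---|---|---|
| 0 | 9.75% | 4.94% | 4.94% | 2.48% |
| 0.5 | 9.07% | 4.65% | 4.54% | 2.32% |
| 0.7 | 8.35% | 4.30% | 4.17% | 2.15% |
| 0.9 | 7.04% | 3.62% | 3.52% | 1.81% |

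At correlation 1 the either-direction rates are 5% and 2.5%. That ratio stays between 1.94 and 2.00 over the whole range from 0 to 1, so the doubling does not depend on the unknown correlation.

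**3. Width of the interval.** The normal critical values are 2.241 for 97.5% and 1.960 for 95%, and 2.241 / 1.960 = 1.144, so the protocol's interval is about 14% wider.

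**4. Illustration on the outcome scale.** As a simple two-sample comparison:
- SE = 0.10 × √(1/66 + 1/67) = 0.01734
- 95%: t(131) = 1.978, half-width 1.978 × 0.01734 = 0.0343
- 97.5%: t(131) = 2.267, half-width 2.267 × 0.01734 = 0.0393

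On these assumptions an estimated gain of about 3.4 to 3.9 percentage points would exclude zero under the SAP and not under the protocol. The SAP fits a spline mixed model whose standard error is not given, and the SD of 0.10 was taken from a similar earlier measure, so this band is only indicative.

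**The case against.** The strongest reply is that the documents establish a mismatch in interval level, not an inflated error rate. The SAP states no alpha. A 95% CI can be a reporting choice, and the protocol's 0.025 might still govern the tests. This stands as a limit: the error figures apply only if 0.05 is the threshold in use. It does not remove the mismatch, because the protocol also committed to 97.5% intervals and the SAP does not report them.

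Second, the SAP's question joins the two outcomes with 'and', and the performance benchmark in protocol C5 requires both measures to reach the cut-off. If a claim of benefit needed both outcomes to be significant, 0.05 each would need no adjustment. But neither document states such a rule for the primary aim, and the protocol's split of alpha points the other way.

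Third, the aim is directional. Even at 0.05 per test, a false claim in favour of A/F has a probability of at most 4.94%, so the absolute rise is about 1.7 to 2.5 percentage points over the correlations tabulated. That is a fair reading of the size; the ratio is still about two.

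Fourth, the protocol's rule was written for sui2 and csra1 in a linear regression of change between two time points, whereas the SAP models eCSSRS1 and eCSRE1 monthly. That these cover the same two care steps is inferred from their names. The reason for the split, however, was the number of primary outcomes, and that is still two.

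Finally, the error rates assume that each test has its nominal size. If the SAP's model misstates the standard error, wider intervals alone would not restore 4.94%.

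**Conclusion.** The concern holds. The SAP replaces the protocol's 97.5% intervals for the two primary outcomes with 95% intervals and gives no alpha, correction or reason. That part rests on the text alone.

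The consequence is conditional on three assumptions: significance is judged at 0.05 per test, either outcome can support a claim, and each test has its nominal size. The chance of at least one false finding then roughly doubles, from 4.94% to 9.75% for independent outcomes and from 3.62% to 7.04% at a correlation of 0.9. The primary conclusion changes only if a p-value falls between 0.025 and 0.05, and the documents do not show whether one does. This should nevertheless be corrected before the primary results are relied on, because it concerns the pre-specified error control of the primary aim.

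**What to change.** In the SAP's Primary Aim, report the differences in change for eCSSRS1 and eCSRE1 with 97.5% CIs, state alpha 0.025 per outcome, and judge each outcome at that level. If the sponsor departs from this, the SAP should say so and justify it. Keep 95% CIs for Secondary Aims 2a and 2b, in line with the protocol. Do not adopt a different multiplicity procedure now, since the data are already complete.

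The cost is one sentence in the SAP and a re-run of the interval calculation with no new data. The primary intervals become about 14% wider, and the point estimates do not change.
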